7. RECRUITMENT RATES AND MILESTONES

7.1 Recruitment rates

Figure 1 shows the projected recruitment of centres and participants, and projected number of women to be approached. Three centres will be established relatively early in the project (by three months) followed by roll out to the others over the subsequent 15 months.

The participant recruitment graph in Figure 1 has been modelled to take into account: the phased rollout to the centres over the first 18 months; that there will be lags between the approach to women when they are in hospital for pre-assessment and their admission for operation; and that there are likely to be fewer operations around August and over Christmas (due to holidays). Randomisation continues after the final recruitment because of these 'lags'.

[figure not shown]

In summary, we aim to recruit around 2250 women to the randomised trials, and a further 2250 to the non-randomised Comprehensive Cohort. This amounts to 300 women per centre (15 sites) over an average recruitment period of 18 months, half of whom will be randomised.

7.2 Revised recruitment rates with extension

Due to the lower than expected recruitment rates, a 12 month extension to the recruitment phase has been approved by the TSC and DMC oversight groups and Funder (December 2011). A revised recruitment graph detailing changes to the primary RCT, secondary RCT and comprehensive cohort is shown in Figure 1a.

Figure 1a Revised projected recruitment chart

In summary, we aim to randomise 1450 woman to the primary repair RCT, 174 women to the secondary repair RCT and enter 1624 into the non-randomised Comprehensive Cohort.

7.3 Project timetable and milestones

Before Start	Agree surgical protocols, standardisation of surgical procedures and		
	mesh options by consensus between Research Committee of BSUG		
	and grant holders.		

Year One	
By month 1	NRES approval
By month 3	Set up office and administrative base
	Construct customised web-based database, including randomisation program and link to BSUG Database
By month 5	Establish first three centres
	(NRES approval, R&D negotiations, train and appoint local
	Recruitment Officers)
By month 6	First Steering Committee Meeting
	Finalise study documentation, training and teaching materials,
	questionnaires
By month 12	First Data Monitoring Committee meeting
	Roll out to further 6 centres (R&D approvals, appoint local Recruitment Officers)

Year Two	
By month 15	First 3 centres fully active, next 8 centres initiated, 610 women recruited to RCTs, 610 to non-randomised Comprehensive Cohort
	Second Steering Committee meeting
By month 18	Establish last 4 centres (R&D approvals, appoint local Recruitment Officers)
	Collaborators' Meeting
By month 24	1598 women recruited to RCTs, 1598 to non-randomised Comprehensive Cohort Second Data Monitoring Committee meeting

Year Three

By month 30 Recruitment complete, 2070 women recruited to RCTs, 2070 to non-

randomised cohort)

Third Steering Committee meeting

By month 36 Third Data Monitoring Committee meeting

Year Four

By month 42 Follow up of women at 12 months after randomisation completed

(primary end point)

Fourth Steering Committee meeting

Year Five

By month 54 Follow up at 24 months after randomisation completed (secondary

end point)

Data collection completed, data cleaning finished

Final Steering Committee meeting

By month 56 Data analysis completed

By month 60 Data archiving, arrangements for long term follow up

Final Collaborators' Meeting

Submit Final Report and dissemination via main papers describing

the study

7.4 Revised timetable and milestones with extension

Year Three

By month 28 All centres fully active

By month 33 Sixth Steering Committee meeting

By month 36 1104 women recruited to the primary repair arm, 132 to the

secondary repair arm and 1236 in the non-randomised cohort.

Third Data Monitoring Committee meeting

Year Four

By month 42 Recruitment complete, 1450 women recruited to the primary repair

arm, 174 to the secondary repair arm and 1624 in the non-

randomised cohort.

Seventh Steering Committee meeting

By month 48 Fourth Data Monitoring Committee meeting

Year Five

By month 54 Follow up of women at 12 months after randomisation completed

(primary end point)

Eighth Steering Committee meeting

Year Six

By month 66 Follow up at 24 months after randomisation completed (secondary

end point)

Data collection completed, data cleaning finished

Final Steering Committee meeting

By month 68 Data analysis completed
By month 72 Data archiving, arrangements for long term follow up
Final Collaborators' Meeting
Submit Final Report and dissemination via main papers describing
the trials

8 ORGANISATION

A detailed plan and timetable of study organisation is given in the Gantt chart (Appendix V).

The Gantt chart indicates when it is anticipated that the major study events will occur, including recruitment, study progress and meetings. There will be 3-monthly project management meetings, nine meetings of the Steering Committee and four of the Data Monitoring Committee. Two meetings are planned for collaborators (including gynaecologists, local recruitment officers, consumer participants and members of BSUG), the first timed to occur when all the sites have been identified and the second when results are available.

These time-related milestones will be used to enable close monitoring of progress.

8.1 Local organisation in centres

i) Lead Gynaecologist (Local Principal Investigator)

Each collaborating centre will identify a Lead Gynaecologist who will be the point of contact for that centre. The responsibilities of this person will be to:

- establish the study locally (for example, by getting agreement from clinical colleagues; facilitate local regulatory approvals; identify, appoint and train a local Recruitment Officer; and inform all relevant local staff about the study (eg other consultant gynaecologists, junior medical staff, secretaries, ward staff))
- take responsibility for clinical aspects of the study locally (for example if any particular concerns occur)
- explain the different surgery options to women and ensure informed consent to randomisation or (if not suitable) follow up in the Comprehensive Cohort study has been obtained
- notify the Study Office of any unexpected clinical events which might be related to study participation
- provide support, training and supervision for the local Recruitment Officer(s)
- represent the centre at the collaborators' meetings.

ii) Local Recruitment Officer

Each collaborating centre will appoint a local Recruitment Officer to organise the day to day recruitment of women to the study. The responsibilities of this person will be to:

- keep regular contact with the local Lead Gynaecologist, with notification of any problem or unexpected development
- maintain regular contact with the Study Office
- keep local staff informed of progress in the study
- contact potential participants by: mailing out the Patient Information Sheet to
 women being admitted electively for prolapse surgery; identifying all eligible
 women at pre-assessment clinics or on the ward while they are in hospital for
 their prolapse surgery; explain the study and the potential for participation in a
 trial if they are eligible; explaining what is intended by research access to their
 NHS data; and describing the possibility of long-term follow up and
 participation in other research
- obtain the woman's written consent to participation (and randomisation as appropriate)

- keep a log of whether eligible women are recruited or not (with reasons for non-participation and non-randomisation)
- collect baseline data describing the women, log this information in the webbased PROSPECT database and send paper copies to the Study Office along with the original signed consent forms
- use this information to randomise the women using the web-based PROSPECT database or the linked telephone randomisation service
- ensure operative and postoperative data are collected and recorded in the web-based PROSPECT database or the BSUG database as appropriate, and send paper copies to the Study Office
- file relevant study documentation (eg consent forms, POP-Q results) in the woman's medical records
- organise and supervise alternative recruiters in case of holiday or absence
- represent the centre at the collaborators' meetings.

8.2 Study co-ordination in Aberdeen

i) The Study Office Team

The Study Office is in CHaRT, Health Services Research Unit in Aberdeen and provides day to day support for the clinical centres. It is responsible for all data collection (such as mailing questionnaires), follow-up, data processing and analysis. It is also responsible for randomisation, and communicating with the sites about PROSPECT specific issues. We will produce a yearly PROSPECT Newsletter for participants and collaborators to inform everyone of progress and maintain enthusiasm.

The PROSPECT Study Office Team (Aberdeen-based grant holders and study office members) will meet formally at least monthly during the course of the study to ensure smooth running and trouble-shooting.

ii) The Project Management Group (PMG)

The study is supervised by its Project Management Group. This consists of the grant holders and representatives from the Study Office. Observers may be invited to attend at the discretion of the Project Management Group. We plan to meet or hold a teleconference every three months on average.

iii) The Trial Steering Committee (TSC)

The study is overseen by an independent Steering Committee. The membership comprises of the four independent members (including the Chairman), the CI and grantholders. Observers or members of the host university (Aberdeen) and the funders (the HTA) may also attend, as may other members of the PROSPECT Study Office or members of other professional bodies at the invitation of the Chair. It is anticipated the TSC will meet on nine occasions.

8.3 Research Governance, Data Protection and Sponsorship

8.3.1 Research Governance

The trial will be run under the auspices of CHaRT based at the Health Services Research Unit, University of Aberdeen. CHaRT is a registered Clinical Trials Unit with particular expertise in running multicentre RCTs of complex and surgical interventions. The study will be conducted in line with local implementation of Research Governance to at least the standard of the Aberdeen University policy on Research Governance

(http://www.abdn.ac.uk/iahs/research-governance/index.shtml).

CHaRT will provide centralised trial administration, database support and economic and statistical analyses.

8.3.2 Data Protection

The trial will comply with the Data Protection Act 1998 and regular checks and monitoring are in place to ensure compliance. Data are stored securely in

accordance with the Act and archived to a secure data storage facility. The consent form will state that other researchers may wish to access (anonymised) data in the future. The trial statistician (in collaboration with the Chief Investigator) will manage access rights to the data set. Prospective new users must demonstrate compliance with legal, data protection and ethical guidelines before any data are released. We anticipate that anonymised trial data will be shared with other researchers to enable international prospective meta-analyses.

8.3.3 Sponsorship

The study is sponsored by the University of Aberdeen.

The CI will ensure, through the TSC, that adequate systems are in place for monitoring the quality of the study (compliance with GCP) and appropriate expedited and routine reports of adverse effects, to a level appropriate to the risk assessment of the study.

8.3.4 Retention of data

It is intended to follow up the whole cohort of women for at least 10 years, and data will be retained as long as necessary for this purpose. Permissions will be sought from the relevant Research Governance bodies and the Ethics Committee. Attention has recently been drawn to the importance of long-term follow up, especially in the study of pelvic floor dysfunction.¹³

8.4 Data and safety monitoring

8.4.1 Data Monitoring Committee

A separate and independent Data Monitoring Committee (DMC) will be convened. It is anticipated the members will meet once to agree terms of reference and on at least three further occasions to monitor accumulating data and oversee safety issues. This Committee will be independent of the study organisers and the TSC. During the period of recruitment to the study, interim analyses will be supplied, in strict confidence, to the DMC, together with any other analyses that the committee may request. This may include analyses of data from other comparable trials. In the light of these interim analyses, the DMC will advise the Steering Committee if, in its view:

- a) one of the methods of prolapse surgery has been proved, beyond reasonable doubt, to be different from the control (standard management) for all or some types of women (in respect of either effectiveness or unacceptable safety concerns), and
- b) the evidence on the economic outcomes is sufficient to guide a decision from health care providers regarding recommendation of which operation to choose.

The TSC can then decide whether or not to modify intake to the trial. Unless this happens, however, the TSC, PMG, clinical collaborators and study office staff (except those who supply the confidential analyses) will remain ignorant of the interim results.

The frequency of interim analyses will depend on the judgement of the Chairman of the DMC. However, we anticipate that there might be two interim analyses and one final analysis.

The Chairman and the other independent members are to be appointed after confirmation by the HTA.

_

Appropriate criteria for proof beyond reasonable doubt cannot be specified precisely. A difference of at least three standard deviation in the interim analysis of a major endpoint may be needed to justify halting, or modifying, such a study prematurely (Peto R et al, *Br J Cancer* 1976;34:548-612).

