There is no evidence to suggest whether or not the use of mesh (particularly non-absorbable synthetic mesh which has the strongest mechanical strength and remains in situ indefinitely) should be reserved for more complex or recurrent prolapse. Although gynaecologists have stated that this is their belief and practice, ³⁰ evidence suggests that the majority (70%) of the current recipients of mesh are having their first prolapse operation. ⁴ An Interventional Procedures review with 503 women ⁴ and a further recent case series of 289²⁶ women drew attention to the high incidence of serious adverse effects (e.g. 2.8% with damage to surrounding organs) in women having mesh inserted with blind introducer devices. Our opinion is that until their benefits and risks have been properly evaluated, mesh kits using non-absorbable synthetic mesh should be reserved for more complex cases of prolapse. Therefore we will limit this option to women being treated for a recurrence of prolapse in the same site after primary surgery.

The initial purchase cost of mesh inlays (around £200 per woman) and mesh kits (around £400-600) is likely to have a significant impact on the cost of prolapse surgery. The proposed trial will provide evidence to indicate whether the extra costs of mesh are justified in terms of better outcomes for women and for the NHS.

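### Protocol 8.4.1 joins the DMC's safety criterion to an economic criterion with 'and', so on a literal reading unacceptable harm alone does not meet the rule for advising the TSC

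*Protocol*

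**What the plan says.** Protocol 8.4.1 states that, in the light of the interim analyses, "the DMC will advise the Steering Committee if, in its view", two lettered conditions hold.

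- Condition (a): a method of surgery has been proved, beyond reasonable doubt, to differ from control for all or some women, "in respect of either effectiveness or unacceptable safety concerns), and".
- Condition (b): "the evidence on the economic outcomes is sufficient to guide a decision from health care providers regarding recommendation of which operation to choose".

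The consequence follows directly: "The TSC can then decide whether or not to modify intake to the trial". The default is also stated. "Unless this happens, however, the TSC, PMG, clinical collaborators and study office staff" stay unaware of the interim results, apart from those who prepare them.

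A footnote says that proof beyond reasonable doubt cannot be specified precisely, and offers a guide: "A difference of at least three standard deviation in the interim analysis of a major endpoint may be needed" to justify halting or modifying the study. It does not distinguish harm from benefit.

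The SAP has no section on interim monitoring or stopping, so it does not qualify this rule.

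**The concern.** The either/or sits inside condition (a). The link from (a) to (b) is 'and'. A DMC that followed the sentence to the letter could find that an operation raises unacceptable safety concerns and still not have met the stated condition for advice, because the economic evidence was not yet sufficient. The TSC, which is the body that can modify intake, would then not be told.

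This matters because safety was a live question in this trial. Appendix I, section 1.3, says that earlier evidence on mesh inserted with blind introducers "drew attention to the high incidence of serious adverse effects (e.g. 2.8% with damage to surrounding organs"). Section 3.1 restricts mesh kits to secondary procedures partly because data on them were scarce.

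The expedited reporting route does not fill the gap. Section 8.4.3 defines a serious adverse event as both related and unexpected, and 8.4.2 lists organ or vessel injury, sepsis and mesh erosion as expected. Such harms reach the DMC through the case report forms. They do not fall under the 15-day report in 8.4.4. For them, 8.4.1 is the only stated route from accumulating data to a change in intake.

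**Working it through.** There is no sample size or error rate to reproduce here; the check is of the rule's logic.

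**Step 1. The rule as a logical statement.** Let S = unacceptable safety concern established, E = difference in effectiveness established, C = economic evidence sufficient. Three versions are compared:

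- as written: (E or S) and C;
- list reading ('and' merely separates two independent triggers): E or S or C;
- separated: S or (E and C).

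| S | E | C | As written | List reading | Separated |
|---|---|---|---|---|---|
| 0 | 0 | 0 | no | no | no |
| 0 | 0 | 1 | no | yes | no |
| 0 | 1 | 0 | no | yes | no |
| 0 | 1 | 1 | yes | yes | yes |
| 1 | 0 | 0 | **no** | yes | **yes** |
| 1 | 0 | 1 | yes | yes | yes |
| 1 | 1 | 0 | **no** | yes | **yes** |
| 1 | 1 | 1 | yes | yes | yes |

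The literal rule and the separated rule differ in two of eight cases, both with harm established and economics insufficient. The literal and list readings differ in four of eight. The list reading would also let economic evidence alone trigger advice, so it is not obviously what was meant either.

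**Step 2. Is there a safety-only criterion elsewhere?**

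- 8.4.1 gives the DMC a general remit over safety and any analyses it asks for. No criterion for advice is attached.
- 8.4.2 sends the listed occurrences to the DMC. No action rule.
- 8.4.4 sends confirmed related and unexpected events to the ethics committee, the sponsor and the DMC within 15 days, and relays concerns to the DMC chair. No action rule.
- 8.3.3 makes the chief investigator responsible, through the TSC, for adverse-effect reporting. No action rule.
- SAP: nothing on the point.

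These routes bring information to the DMC. None says when the DMC should pass a safety judgement on.

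**Step 3. When can (b) be met?** Under 6.5.1, theatre resources are recorded at surgery, length of stay and readmissions go on the case report form, and the utilisation questionnaire is given at baseline, 12 and 24 months. Under 6.5.3, EQ-5D is collected at baseline, 6, 12 and 24 months. Under 6.5.4, the primary economic analysis uses one-year follow-up. Intra-operative and early post-operative harm is visible within days. Condition (b) is therefore likely to mature later than (a) for harm of this kind. No fixed interval follows, because 8.4.1 sets no follow-up requirement for (b).

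**Step 4. The three-standard-deviation guide.** Taken as three standard errors of the difference, it corresponds to a two-sided p of 0.0027. To see how it would behave if applied to a rare harm, take the planned 206 women per arm in the secondary trial (Protocol Table 1), no events on standard repair, and a pooled two-proportion z.

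- 9 v 0: pooled p = 9/412 = 0.0218; SE = √(0.0218 × 0.9782 × 2/206) = 0.0144; z = (9/206)/0.0144 = 0.0437/0.0144 = 3.03.
- 8 v 0: pooled p = 8/412 = 0.0194; SE = 0.0136; z = 0.0388/0.0136 = 2.86.

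Nine events (4.4%) would be needed. At the cited 2.8% organ-damage rate, 0.028 × 206 = 5.8 would be expected. This is an illustration only. It shows why the footnote should say that it concerns effectiveness.

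**The case against.** The strongest reply is that 8.4.1 says the DMC will advise if the conditions hold, not that it may advise only then. The conditions are assessed in the DMC's own view. It has a safety remit and a flow of harm reports, and its terms of reference, agreed separately, are not among the documents. The 'and' may be no more than a list connector, and a sensible DMC would very probably speak up about harm. Much of this stands: it makes it likely that the wording, not the intent, is at fault. It does not supply the missing criterion, and the default that keeps the TSC blind is explicit.

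Three stronger readings are tempting, and the documents do not support them.

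- A reader might infer that this rule is all that limits exposure to mesh kits. It is not. Sections 2.4 and 3.1 and Appendix I (1.3 and 1.4) restrict kits to secondary repairs and to surgeons trained beyond the learning curve.
- A reader might infer a fixed 12-month delay to any safety advice. Step 3 shows that some economic data arrive sooner, and sufficiency is a matter of DMC judgement.
- A reader might take the final numbers in SAP Table 3 (stratum RCT2: 44 mesh kit, 24 standard) and conclude that 14 of 44 kit women (32%) would have to be harmed before the DMC could act. The guide is non-binding, organ injury is a secondary outcome in 6.2 and nothing applies the guide to it, and those numbers reflect under-recruitment that was known only later.

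It is also fair to say that Appendix IV reports recruitment from January 2010 to August 2013. Rewording an intake rule now cannot change any woman's allocation, and nothing shows that the DMC read the rule literally.

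**Conclusion.** The point holds for the rule as written. The only stated criterion for DMC advice on accumulating data requires sufficient economic evidence even when the ground for advice is unacceptable harm. Its size is logical, not numerical: the rule gives no advice in the two of eight combinations where harm is established and the economics are not. The economic condition probably matures later than peri-operative harm, so these are realistic situations early in recruitment.

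The conclusion rests on reading 'and' in its ordinary sense and on the absence of a safety-only criterion in the protocol and SAP. The DMC terms of reference could contain one. It does not rest on the three-standard-deviation arithmetic, and it does not imply that the DMC was barred from acting or that any woman was harmed by the wording. DMC advice also leads to a TSC decision on whether to modify intake; it does not itself stop an operation.

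**What to change.** Reword 8.4.1, and match the DMC terms of reference to it, so that the two grounds are separate.

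- The DMC may advise the TSC if, in its judgement, an operation raises unacceptable safety concerns. No economic condition applies.
- The DMC advises the TSC on effectiveness if a difference is established beyond reasonable doubt and the economic evidence is sufficient.
- The footnote's three-standard-deviation guide stays non-binding and is stated to apply to effectiveness.

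The sentence that keeps the TSC blind should then refer to either ground. Because recruitment has closed, it would also help to record in the trial report which reading the DMC worked to.

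The cost is a wording change, with no extra data, participants or staff. The small downside is that safety advice then rests on DMC judgement and not on a numerical threshold.
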